7.8. Repeat Cryoablation Treatment(s) or Alternative Additional Treatment

Patients may receive additional cryoablation treatment(s) to the index tumor(s) initially subjected to cryoablation while participating in the study protocol. This additional cryoablation may be performed on the index tumor(s) provided that the additional treatment is performed with Galil Medical technology. In this situation, for each index lesion retreated, follow-up visits will restart per the study protocol and continue through the 24 month visit after the date of the repeat cryoablation treatment. When possible, if multiple tumors are present, all efforts should be made to align all follow up visits. For any index lesion not subjected to retreatment, the data collection continues per protocol.

- Baseline labs are recommended to be repeated prior to any repeat cryoablation procedure;
- It is recommended to discontinue anticoagulation as clinically indicated;

- SF-12 will not be collected prior to or after any repeat cryoablation of index tumor(s);
- Pertinent medications should be reviewed prior to and after any repeat cryoablation of index tumor(s);
- All other follow-up requirements are still applicable.

If other local treatment (e.g. radiofrequency ablation, microwave ablation, surgery, radiation) is used on the index tumor(s) initially treated, then the patient must be withdrawn from the study.

Data will be collected regarding any systemic cancer therapy the patients receive during the course of the study.

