7.9. Study Completion or Withdrawal

Patients may withdraw from this study at any time, with or without a reason, without prejudice to further treatment. Investigators should make every effort within the bounds of safety and patient choice to have each patient complete the study. If a patient does not return for a scheduled visit, every effort should be made to contact the patient. In any circumstance, every effort should be made to document patient outcome, if possible. The investigator should inquire about the reason for withdrawal; request the patient return for a final visit, if applicable, and follow-up with the patient regarding any unresolved adverse events. If possible, the reason(s) for withdrawal (if given) will be recorded.

If the patient withdraws from the study and also withdraws consent for disclosure of future information, no further evaluations should be performed and no additional data should be collected. The sponsor may retain and continue to use any data collected before such withdrawal of consent.

Patients who request Early Termination from the study will be asked to return if physically capable for a final visit to complete the following assessments.

- Karnofsky Performance Scale;
- Chest CT scan, \pm contrast (contrast is preferred);
- Safety assessment;
- Assessment of metastatic lung disease progression, including additional treatment;
- Assessment of any new cancer treatment(s).

In the event the patient enters hospice or another similar care program, early termination should be documented. Information taken from the medical record is sufficient to document this reason for early termination in the event this communication is not provided by the patient.

Patients may be considered "lost to follow-up" after 3 unsuccessful attempts to contact the patient with one contact being a registered letter to the last known address of the patient. Site should document all attempts to contact the patient in the source documents.

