10.5.3. Primary Endpoint

The primary endpoint for this study is defined as follows: efficacy of cryoablation on local tumor control for each index tumor in patients with pulmonary metastatic disease at 12 months post cryoablation.

Patients are allowed up to 6 tumors and the primary efficacy endpoint (tumor control) will be calculated on a per tumor level. To be considered a success each tumor treated during the baseline procedure must meet the tumor control criteria at the 12 month follow-up visit.

The local tumor control counts and rates will be presented along with the 95% two-sided confidence intervals for the rates. The rate numerator will be defined as the number of tumors experiencing tumor control at 12-months. The rate denominator will be defined as the total number of tumors evaluated at 12-months.

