- **Time to overall cancer progression** is defined as the time in days from the first cryoablation procedure to cancer progression (i.e., any location of active cancer disease). Patients without cancer progression will be censored at the date of their last visit or their date of death (due to any cause). Overall cancer progression free survival rates will be summarized by using Kaplan-Meier methodology.
- **Time to untreatable metastatic lung disease control with cryoablation** is defined as the time in days from the first cryoablation procedure to the time when the metastatic lung disease cannot be treated with cryoablation. Overall time to untreatable metastatic lung disease progression rates will be summarized by using Kaplan-Meier methodology.
- **Time to untreatable metastatic lung disease control with focal therapy** is defined as the time in days from the first cryoablation procedure to the time when the metastatic lung disease cannot be treated by focal (e.g., ablation, surgery, SBRT) intervention for control of metastatic lung disease. Overall time to untreatable metastatic lung disease progression rates will be summarized by using Kaplan-Meier methodology.

Intra-procedural data

Initial cryoablation procedure information including the tumor size and number, cryoablation needle type and the number of each type of needle used, freeze and thaw times, procedure times, and anesthesia type.

Physical performance and quality of life

Physical performance (KPS) and quality of life (SF-12) assessments will be made by examining the change in the baseline scores to those reported post-operatively as defined in Sections 8.4 and 8.5, respectively.

Subset Analyses

Analysis may be done on outcomes for subgroups including, but not limited to, gender, primary cancer and tumor size.

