The safety endpoint for this study is to assess the incidence and severity of intra-operative events, post-operative adverse events, serious adverse events and unanticipated adverse device effects related to the cryoablation procedure.

No formal hypothesis test is being made on the safety endpoints. Point estimates and two-sided 95% confidence intervals will be generated for cryoablation related adverse events.

Supportive Endpoint Analyses

Tumor control (patient level & weighted average response)

The primary efficacy endpoint is on a lesion basis. Analysis on a patient level will also be conducted in two ways. 1) Patient level: A patient must exhibit tumor control on all lesions to be considered a success using logistic regression analysis to calculate success rate and Wald 95% CI. 2) Weighted average response: patient level response rate weighted by the number of lesions that are evaluated. This will be reported as a proportion (number of successful lesions over the total number of lesions) and a 95% exact CI.

Tumor control (pulmonary metastatic disease)

Efficacy of cryoablation on local tumor control in patients with pulmonary metastatic disease at 18 and 24 months post cryoablation using a random effects logistic regression model to account for the correlation among multiple tumors per subject.

Tumor control (additional cryoablation)

Patients may receive additional cryoablation treatment(s) to the index tumor(s) initially subjected to cryoablation while participating in the study protocol. This additional cryoablation may be performed on the index tumor(s) provided that the additional treatment is performed with Galil Medical technology. In this situation, for each index lesion retreated, follow-up visits will restart per the study protocol and continue through the 24 month visit after the date of the repeat cryoablation treatment. When possible, if multiple tumors are present, all efforts should be made to align all follow up visits. For any index lesion not subjected to retreatment, the data collection continues per protocol. If additional local treatment (e.g. radiofrequency ablation, microwave ablation, surgery, radiation) is required, then the patient must be withdrawn from the study.

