- **Time to metastatic lung disease progression beyond the index tumor** is defined as the time in days from the first cryoablation procedure to metastatic disease beyond the index tumor site. Patients without metastatic lung disease progression will be censored at the date of their last visit or their date of death (due to any cause). Metastatic progression free survival rates will be summarized by using Kaplan-Meier methodology.
- **Time to overall cancer progression** is defined as the time in days from the first cryoablation procedure to cancer progression (i.e., any location of active cancer disease). Patients without cancer progression will be censored at the date of their last visit or their date of death (due to any cause). Overall cancer progression free survival rates will be summarized by using Kaplan-Meier methodology.
- **Time to untreatable metastatic lung disease control with cryoablation** is defined as the time in days from the first cryoablation procedure to the time when the metastatic lung disease cannot be treated with cryoablation. Overall time to untreatable metastatic lung disease progression rates will be summarized by using Kaplan-Meier methodology.
- **Time to untreatable metastatic lung disease control with focal therapy** is defined as the time in days from the first cryoablation procedure to the time when the metastatic lung disease cannot be treated by focal (e.g., ablation, surgery, SBRT) intervention for control of metastatic lung disease. Overall time to untreatable metastatic lung disease progression rates will be summarized by using Kaplan-Meier methodology.

Intra-procedural data

Initial cryoablation procedure information including the type of procedure, tumor size and number, cryoablation needle type and the number of each type of needle used, freeze and thaw times, procedure times, and anesthesia type will be summarized using descriptive statistics.

Physical performance and quality of life

Physical performance (KPS) and quality of life (SF-12) assessments will be made by examining the change in the baseline scores to those reported post-operatively and at follow-up visits. The KPS scale and each of the eight SF-12 domains will be summarized at each time point by descriptive statistics. Percent change from baseline for each measure will also be summarized by descriptive statistics.

Additional Data Summaries

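### Other local therapy to one index tumor withdraws the whole patient, so untouched tumors lose later readings and the focal-therapy outcome is no longer observed in that patient

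*Protocol*

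**What the plan says.** Protocol 7.8 covers two kinds of further treatment to an index tumor and handles them differently.

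- **Repeat cryoablation.** The retreated lesion restarts its visit schedule. The others stay in: "For any index lesion not subjected to retreatment, the data collection continues per protocol".
- **Other local treatment** (the examples are radiofrequency or microwave ablation, surgery and radiation). If this "is used on the index tumor(s) initially treated, then the patient must be withdrawn from the study".

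The SAP, under Tumor control (additional cryoablation), has the same rule with a different trigger. Withdrawal follows if such treatment "is required, then the patient must be withdrawn from the study", and that sentence does not limit it to index tumors. Protocol 7.10 adds that participation is discontinued for supplemental treatment that may affect the primary efficacy outcome.

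The unit of the primary analysis is the tumor: "Patients are allowed up to 6 tumors and the primary efficacy endpoint (tumor control) will be calculated on a per tumor level" (Protocol 10.5.3). The denominator there is tumors evaluated at 12 months. The SAP instead imputes missing month-12 readings by multiple imputation from prior tumor status. Its one override is that failure at month 6 counts as failure at month 12.

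Among the other outcomes in Protocol 10.5.5 is the time until lung disease "cannot be treated by focal (e.g., ablation, surgery, SBRT) intervention for control of metastatic lung disease". The SAP says of it: "Overall time to untreatable metastatic lung disease progression rates will be summarized by using Kaplan-Meier methodology". Neither document gives a censoring rule for it. Overall survival is censored at the last visit in patients who are alive.

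**The concern.** The unit of removal is the patient and the unit of analysis is the tumor. When one of several index tumors is resected or irradiated, scheduled follow-up also stops for tumors to which nothing was done. The protocol gives no reason for treating them differently from untouched tumors after repeat cryoablation.

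Three things are at stake.

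1. **Primary endpoint.** An untouched tumor with no month-12 reading drops out of the protocol's denominator or is imputed under the SAP. The imputation model names prior tumor status and nothing about the reason for leaving.
2. **Focal-therapy outcome.** Using one of the therapies that define this outcome on an index tumor ends observation, so any later event in that patient goes unseen.
3. **Survival.** It is cut at the last visit in the same patients.

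Other local therapy to an index tumor probably follows recurrence or progression. Censoring at that moment is therefore likely to be informative, and Kaplan-Meier estimates assume that it is not.

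**Working it through.** **Step 1: the plan's own figures.** Inputs from Protocol 10.1 and section 5: null rate 0.84, alternative 0.91, 203 tumors, reject at 181 or more successes, 10% attrition, 226 tumors, 150 patients.

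- P(X >= 181 | n = 203, p = 0.84) = 0.0239 and P(X >= 181 | n = 203, p = 0.91) = 0.8501. Both match the plan.
- 203 / 0.90 = 225.6, rounded up to 226. The allowance is 226 - 203 = 23 tumors.
- 226 / 150 = 1.51 tumors per patient.

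**Step 2: readings lost.** Let w be the share of patients given other local therapy before month 12. The documents give no value, so 5%, 10% and 15% are assumptions. Assume one treated tumor per affected patient and the planned mean number of tumors.

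- All tumors lost = 150w x 226/150 = 226w
- Treated tumors = 150w
- Untouched tumors = 226w - 150w = 76w

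| w | Patients | All tumors lost | Treated | Untouched | Untouched as share of 23 |
|---|---|---|---|---|---|
| 5% | 7.5 | 11.3 | 7.5 | 3.8 | 17% |
| 10% | 15.0 | 22.6 | 15.0 | 7.6 | 33% |
| 15% | 22.5 | 33.9 | 22.5 | 11.4 | 50% |

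The cost of withdrawing the patient rather than the tumor is the untouched column. It depends on how many tumors affected patients carry. With 2 to 3 each, which the documents do not support or exclude, the range at 5-10% would be 7.5 x 1 = 7.5 to 15 x 2 = 30. A 6-tumor patient loses up to 5 untouched readings.

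**Step 3: power.** Suppose the untouched losses come on top of the full 10% attrition and are simply dropped. Exact one-sided test, alpha at most 0.025, alternative 0.91:

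- w = 5%: 203 - 3.8, about 199 tumors, power 0.815
- w = 10%: 203 - 7.6, about 195 tumors, power 0.839
- w = 15%: 203 - 11.4, about 192 tumors, power 0.795

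Power moves unevenly because the cut-off is a whole number. If treated tumors are also lost at w = 10%, 203 - 22.6 = 180.4 remain; power is 0.808 at 180 tumors and 0.801 at 181. All figures assume independent tumors, as the SAP's sample size does. Within-patient correlation would lower them.

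**Step 4: what the exit visit recovers.** Table 1 has a column shared with withdrawal that includes CT, performance status and safety. The list in Protocol 7.9 includes CT and "Assessment of metastatic lung disease progression, including additional treatment". It has no item on whether further treatment is feasible, although the visits in 7.5 to 7.7 do. So local status at exit is measurable, and treatability at exit is not on the list. Neither document schedules anything after exit.

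**The case against.** The strongest reply is that the loss is small and partly covered. The SAP does not simply drop missing readings: it imputes them and adds worst-case, best-case and complete-case analyses. At the planned mean, 5-10% of patients cost 4-8 untouched tumors and leave power above 0.80 for independent tumors. The treatability outcomes are listed as other data, with no hypothesis test. All of this stands, and it limits the severity.

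A reader might also infer three stronger things that the documents do not support.

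- **That only patients who ask to leave get an exit visit.** The 7.9 list is attached to those patients. However, the Table 1 column is not limited to them, and the general paragraph of 7.9 asks for a final visit where applicable and for outcome to be documented in any circumstance.
- **That only patients who switch therapy can separate the focal-therapy outcome from the cryoablation-only one.** Both outcomes turn on whether disease can be treated, and feasibility is recorded at scheduled visits. A patient judged unsuitable for cryoablation but suitable for other focal therapy separates the curves there. Under 7.8, therapy to a non-index tumor does not trigger withdrawal, though the SAP sentence and 7.10 could be read more widely.
- **That the rule uses up the attrition allowance through untouched tumors.** This needs 2 to 3 tumors per affected patient, a figure the documents do not give.

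The reply does not remove the mismatch. One exit visit cannot supply a month-12 reading, later treatability or survival, and imputation cannot restore follow-up that the protocol ended.

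**Conclusion.** The point holds at moderate severity: it should be fixed, but it does not by itself undermine the primary test. An untouched tumor loses its month-12 reading only if the patient has more than one index tumor and the therapy comes before the month-12 visit. The SAP revision history records more than 10 subjects with multiple lesions, so such patients exist.

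Under the stated assumptions the loss is about 4-8 untouched tumors at a 5-10% rate of other local therapy, and 11.4 at 15%, against an allowance of 23. It is larger if affected patients carry more tumors than average. The rate itself is unknown from the documents.

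For the focal-therapy outcome, follow-up is truncated at the switch in every patient whose index tumor receives other local therapy, with no censoring rule and with censoring that is probably informative. The outcome stays observable in all other patients.

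**What to change.** These changes concern data collection and analysis only and alter no treatment.

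1. **Protocol 7.8 and the matching SAP sentence.** Replace patient withdrawal with text to this effect: *Local-control follow-up of the index tumor given other local therapy ends. The patient stays in the study, and other index tumors, lung progression, treatability and survival are followed to month 24.*
2. **Reconcile the triggers.** Protocol 7.8 speaks of therapy used on an index tumor, the SAP of therapy that is required, and 7.10 of treatment that may affect the primary outcome. Without this, 7.10 would contradict the new text.
3. **SAP, month-12 status.** State it for the tumor given other local therapy, for example failure in the primary analysis with imputation as a sensitivity analysis. As written, that tumor is imputed unless failure was recorded at month 6. Treat a sibling tumor lying within the resected or irradiated field the same way.
4. **SAP, censoring.** Give a censoring rule for the focal-therapy outcome.
5. **Protocol 7.9.** Add the feasibility-of-treatment item to the exit list.

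The cost is a protocol amendment, a short SAP revision, and already scheduled visits continued for a few patients; no new procedure is added. If follow-up is too far advanced for the protocol change to help, items 3 and 4 can still be settled before analysis.

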7.7. Months 6, 12, 18 and 24 – Follow-up

Patients will return 6, 12, 18, and 24 months (+/-30 days) post cryoablation procedure. In the event of multiple cryoablation procedure dates, the most recent procedure date will serve as the reference for determining the follow up visit window.

The following assessments will be completed:

- Karnofsky Performance Scale;
- Chest CT scan \pm contrast (contrast is preferred);
- Safety assessment;
- Assessment of metastatic lung disease progression beyond the index tumor and feasibility of treatment;
- Assessment of local tumor recurrence at the index tumor, including additional treatment and feasibility of treatment;
- Assessment of any systemic cancer treatment(s);
- Assessment of any local therapy for the index tumor(s).

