8.7.4 Local Failure

Local failure will be defined as $\geq 20\%$ increase in the sum of the three axes of measurements (longest diameter plus the two perpendicular diameters) when compared with the nadir of this 3 axes measurement.

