For the formal primary endpoint hypothesis test, patients with missing 12-month tumor evaluations will be imputed using multiple imputation (SAS PROC MI using FCS logistic regression and including tumor status at prior visits), except in the following case where previous visit evidence can be used to impute 12-month status:

- Subjects with local tumor failure at 6-months will be considered a local tumor failure at 12-months post-index procedure.

Additional sensitivity analyses to be conducted:

- Worst case: all missing data are imputed to be failures
- Best case: all missing data are imputed to be successes
- Complete case: all missing data are treated as missing and not imputed

Subset Analyses

Analysis will be done on outcomes for subgroups including, but not limited to, gender and lesion size. Additional non-protocol defined subgroups include: number of needles used, number of lesions, primary cancer diagnosis, and lesion location.

Poolability Analyses

A poolability analysis among investigational centers and geographies (US/OUS) will be performed for the primary efficacy endpoint. This analysis will be performed on the ITT population.

Poolability of Sites

Combining of Small Sites

Sites contributing less than 5 subjects to the as treated analysis set will be considered “small sites” and ordered by the date of first enrollment in the as treated analysis set. Starting with the first “small site”, a pseudo-site will be created by adding subjects from successive “small sites”. If the number of subjects reaches or exceeds the size of the median enrollment of the “large sites”, then a second pseudo-site will be created. Additional pseudo-sites, if needed, would be created in the same manner.

Primary Endpoint by Site

Among sites and pseudo-sites, the proportions of subjects who achieve local tumor control at 12 months will be compared using logistic regression. If the resulting p-value is ≤ 0.05 , further exploratory analysis will attempt to identify covariates (baseline characteristics) that may explain differences among the sites. Otherwise, the data will be considered to be poolable across study sites.

Poolability of Geographies

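### Withdrawing the whole patient when one index tumour gets other local treatment leaves that tumour's month-12 result to imputation, which can tilt the primary test toward success

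*Protocol*

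**What the plan says.** **Withdrawal.** Protocol 7.8 names radiofrequency ablation, microwave ablation, surgery and radiation as examples of other local treatment. If such treatment "is used on the index tumor(s) initially treated, then the patient must be withdrawn from the study". The SAP, under Tumor control (additional cryoablation), has the matching sentence: if additional local treatment "is required, then the patient must be withdrawn from the study".

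**Repeat cryoablation.** The same section of the protocol handles this at tumour level: "For any index lesion not subjected to retreatment, the data collection continues per protocol".

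**Endpoint.** Protocol 10.5.3 and the SAP allow up to 6 tumours per patient and calculate local control per tumour. Protocol 8.7 defines control as the absence of local failure. Protocol 8.7.4 defines local failure only by measurement, as a 20% or larger "increase in the sum of the three axes of measurements (longest diameter plus the two perpendicular diameters) when compared with the nadir". Neither document says how to score an index tumour that received other local treatment.

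**Missing month-12 results.** For the primary test, the SAP (Handling of Missing Data) uses multiple imputation, "including tumor status at prior visits", with one exception: "Subjects with local tumor failure at 6-months will be considered a local tumor failure at 12-months post-index procedure". Worst-case, best-case and complete-case analyses are planned as sensitivity analyses.

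**What remains at withdrawal.** Table 1 has an imaging scan in the column shared by months 6 to 24 and withdrawal. Protocol 7.9 lists a final CT for patients who ask to leave early, and a general effort to document outcome. No imaging is scheduled after withdrawal.

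**The concern.** Surgery or radiation to an ablated tumour is seldom a random event. The follow-up visits pair the assessment of local recurrence at the index tumour with additional treatment and its feasibility, so the link to local failure is a fair inference, although the documents do not state it.

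Consider a tumour that is controlled at month 6, regrows, and is irradiated at month 9. The patient is withdrawn. The tumour has no month-12 scan, the irradiation is not a failure, and the month-6 rule does not apply. Its month-12 status is imputed with control at month 6 as the informative predictor, so it is treated as if it resembled the controlled tumours still in follow-up. Failures of this kind are replaced mostly by successes, which favours the device in the test against 84%.

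The patient's other index tumours also leave scheduled imaging. That costs information and is avoidable, since 7.8 already follows tumours separately after repeat cryoablation.

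**Working it through.** **1. The plan's own figure.** Exact binomial test, N = 203, success if at least 181 tumours are controlled: alpha at 0.84 is 0.0239 and power at 0.91 is 0.8501. Allowing for 10% attrition, 203/0.90 = 225.6, hence 226. All agree with the documents. The point does not depend on an error here.

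**2. How many tumours share a patient.** Inputs: 226 tumours, 150 patients (Protocol 5), at most 6 each.
- Tumours beyond one per patient: 226 − 150 = 76.
- Fewest sharing: 15 patients with 6 and 1 with 2, so 92 tumours, 92/226 = 41%.
- Most sharing: 76 patients with 2, so 152 tumours, 152/226 = 67%.
- Average number of other index tumours withdrawn with a treated one, Σn(n−1)/226: 152/226 = 0.67 in the second pattern and (15×30 + 2)/226 = 2.0 in the first.

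**3. Effect of unseen failures on the imputed rate (expected values).** Take true control at the 84% goal: 226 × 0.16 ≈ 36 failures. Assume half (18) occur by month 6 and are carried forward, leaving 208 tumours controlled at month 6. If k of the 18 later failures are unseen, imputation from month-6 status gives

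failures = 18 + 208 × (18 − k)/(208 − k), control = 1 − failures/226.

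| k unseen | imputed control |
|---|---|
| 0 | 0.841 |
| 1 | 0.845 |
| 2 | 0.849 |
| 4 | 0.857 |
| 9 | 0.879 |

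Each unseen failure adds about 0.4 percentage points.

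**4. Effect on the test (simulation).** True control 84%; 150 patients (74 with one tumour and 76 with two, or a more uneven spread up to six); within-patient correlation 0.1; 10% of patients lost at random; 10 imputations; 6000 runs. A cluster-robust Wald bound on the logit scale stands in for the SAP's random-effects model. Correlation, timing of failure, share treated elsewhere and share recorded are all assumptions. A later failure that is recorded is counted as a failure at month 12, which is more than the SAP's month-6 rule guarantees.

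Probability of declaring success at a true 84%, by share of failing tumours treated elsewhere:

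| | 0% | 10% | 25% | 50% |
|---|---|---|---|---|
| Patient withdrawn, half of later failures recorded | 0.019–0.021 | 0.028–0.033 | 0.043 | 0.074–0.079 |
| Patient withdrawn, none recorded | 0.019–0.023 | 0.039–0.042 | 0.096–0.104 | 0.312–0.314 |
| Only the treated tumour lost, none recorded | 0.019–0.023 | 0.036–0.041 | 0.086–0.097 | 0.292–0.296 |

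The last two rows nearly coincide, so the treated tumour carries most of the bias. Withdrawing the whole patient mainly adds missing outcomes: 38 to 43 tumours instead of 29 at the 50% share. With the other tumours followed and the treated one scored as a failure, the probability is 0.013 to 0.023 across these settings.

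**5. Why continued scanning alone would not help.** Protocol 8.7.1 counts disappearance of the ablation zone as complete response. If the other treatment makes the zone meet the control criteria and the later scan is used, k = 9 gives 1 − 27/226 = 0.881, against 0.879 under imputation; k = 4 gives 1 − 32/226 = 0.858, against 0.857. The bias would remain.

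**The case against.** The strongest reply is that the plan already has safeguards. There is imaging at withdrawal, 7.9 asks for the outcome to be documented, and the independent panel in 8.7 weighs the overall clinical evaluation in its final determinations. A month-3 failure enters the imputation as a predictor. Repeat cryoablation is allowed without withdrawal, so some local failures never reach this rule. If failure prompted the treatment, it will often have been seen, so assuming that none is recorded is severe.

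Much of this stands, and it is why the half-recorded row is the one to quote. It does not close the gap. The SAP does not say that a failure seen on a withdrawal scan after month 6 counts at month 12, and a tumour treated before it has grown by 20% meets no failure rule at all. The worst-case analysis does count these tumours as failures, but it counts every other missing tumour too: with 10% missing, a true 91% reads as 0.90 × 0.91 = 82%, below the goal.

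A reader might infer that losing all of the patient's tumours is what drives the bias. The last two simulation rows show otherwise. A reader might also see a conflict with 7.10, or read the SAP sentence as reaching tumours other than index tumours. The SAP sentence closes a paragraph on retreatment of index tumours, and 7.8 itself expects systemic therapy during the study. Neither reading is needed for this point.

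**Conclusion.** The point holds as a gap in the plan that is cheap to close. Followed as written, the plan can bias the primary test toward success, because an event plausibly linked to failure removes the tumour from follow-up and no rule scores that event.

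The documents give no rate of other local treatment, so the real size is unknown. With 10 to 25% of failing tumours treated elsewhere, half of all failures after month 6, and half of the later failures among treated tumours recorded and counted, false success is about 3 to 4% against a 2.5% target. If none is recorded it is about 4 to 10% at the same shares. If other treatment is unrelated to failure there is no bias.

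A reader might go further and conclude that the error rate is about 30%. The documents do not support that. The 31% requires half of failing tumours to be treated elsewhere and none of the later failures to be recorded. Complete-case counting gives similarly large values (0.056, 0.17 and 0.32 if 10, 20 and 30% of all failures go missing), but that is a sensitivity analysis in the SAP and not the primary test.

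**What to change.** 1. **Protocol 7.8 and the SAP sentence.** Replace withdrawal of the patient with continued scheduled imaging of the untreated index tumours and survival follow-up to month 24. Record the therapy, the tumour treated and the date.
2. **SAP primary analysis.** Score an index tumour given other local treatment before month 12 as a local failure from that date, and never as controlled on a later scan. Add a sensitivity analysis that treats it as missing from that date.
3. **SAP, Handling of Missing Data.** Extend the month-6 rule to any local failure recorded before month 12, including one on the withdrawal scan.

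**Cost.** A protocol amendment with ethics approval, possibly with consent wording. The imaging is already in the schedule, and items 2 and 3 are SAP wording plus one analysis. The SAP revision history shows that patients with several lesions were already enrolled, so the follow-up change may come mid-study and help only later patients. The estimate becomes slightly conservative if some treatments were given without local failure: each such tumour, if it would otherwise count as controlled, lowers the rate by 1/226, about 0.4 percentage points. The sensitivity analysis in item 2 shows how much this matters.
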